# 9.3 Missing Data

No missing data will be imputed for the primary analysis and secondary analyses.

# 9.4 Statistical Methodology

# 9.4.1 Data Summary

The following is a detailed proposal of statistical analyses planned for data collected during the study.

Descriptive statistics will be computed for all preoperative conditions and demographic parameters. That is, for continuous data (e.g. HHS), the N, mean, median, standard deviation, minimum and maximum will be computed. For categorical data (e.g. gender), the frequency and percentage will be computed.

Descriptive statistics and statistical comparisons for important demographic, efficacy and safety variables will be provided in tables.

A survival analysis will be performed.

### 9.4.2 Sample Size Calculation

A literature review shows that at 10 years of follow-up there is an approximate 97% success rate using postoperative femoral head dislocation as the defining factor. Using a base success rate of 97% from the literature and a delta of 3.5%, it was calculated that 274 total cases would be needed to prove non-inferiority with 95% confidence. With a minimum of 274 cases analyzed, the primary hypothesis of the study will be met if the lower bound of the one-sided 95% confidence interval for the 10-year success rate is greater than 93.5%. By factoring in a 20% lost to follow-up rate within a 10-year period, the required enrollment increases to 343 cases. A total of 350 cases will be enrolled into the study.

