# **Hypothesis**

The success rate, defined as freedom from postoperative femoral head dislocation, for hips implanted with the Restoration® ADM X3® Acetabular System, is not 3.5% worse than hips implanted with other primary hip systems in the literature at 10 years. The success rate for other primary hip systems is approximately 97%. With a non-inferiority margin of 3.5%, the success rate for the Restoration® ADM X3® Acetabular System will be no less than 93.5% at 10 years.

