### 9.4.4 Efficacy Patient Populations

### 9.4.4.1 **Efficacy**

#### Per protocol population:

The study population for analysis will include all subjects who receive the Restoration® ADM Acetabular Shell and Restoration® ADM X3® Acetabular Insert and have the primary efficacy variable measurements available. This does not include cases censored from analysis for a reason that may have a significant impact on outcome.

The primary efficacy analysis will be based on the per protocol population.

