### 9.4.4.4 Censored Cases

In the event that a protocol deviation occurs which could affect subject outcome, the data for the affected subject will be censored from the Efficacy and Safety Subejct Populations. All cases that fall into this category will be reported separately.

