# 10.3 Early Withdrawal of Subjects

### When and How to Withdraw Subjects

In the event that the subject is discontinued by the investigative center prior to the final study evaluation, the subject will be notified by the center that he/she is no longer in the study and a Study Termination eCRF will be completed.

The following is a list of reasons for which subjects may be withdrawn and the date of termination that should be used on the Study Termination eCRF in each situation. This list is not all inclusive:

Termination Reason	Date of Termination
Death	Date of death
Investigative center termination	Date of study close-out visit
Lost to follow-up	Date Stryker termination approval given
Voluntary withdrawal	Date subject notified center of withdrawal
Revision/removal of study device	Date of revision/removal procedure
Study device not implanted	Date of surgery
Surgery not performed	Date Stryker termination approval given

At the time of study surgery it is required that the following components are implanted for each treatment group:

Restoration® ADM X3® System with any compatible Stryker Stem:

- Restoration® ADM Acetabular Shell
- Restoration® ADM X3® Acetabular Insert

- o 28 mm Stryker femoral head (except for the LFIT™ Anatomic CoCr femoral bearing head)
- Compatible Stryker femoral stem (with a minimum of 100 Accolade® II Hip Stems)

Revision or removal of the Restoration® ADM X3® Acetabular System (acetabular shell and insert) constitutes a failure and study termination for the subject.

If femoral stem or femoral head revision is required during the study, the event is considered a reoperation and does not constitute a failure or study termination.

If the subject fails to return for his/her follow-up appointments, every effort should be made to contact the subject to assess his/her health status. If, after attempting to contact the subject through three documented phone calls and a certified letter, the subject still does not respond, he/she will be considered lost to follow-up. A Study Termination eCRF will be completed only after notifying Stryker of the subject's status and being given approval to terminate.

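### The 274-case minimum is protected only against 20% loss to follow-up, leaving 6 cases for every other exit, and a proportion in measured cases would understate the success rate

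*Combined protocol and SAP*

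**What the plan says.** The plan is in section 9.4.2 of the combined protocol and SAP. It starts from the literature ("Using a base success rate of 97% from the literature and a delta of 3.5"), arrives at 274 cases, and sets the criterion as follows: "With a minimum of 274 cases analyzed", success is claimed if the "lower bound of the one-sided 95% confidence interval for the 10-year success rate is greater than 93.5" per cent. It then inflates for attrition: "By factoring in a 20% lost to follow-up rate within a 10-year period, the required enrollment increases to 343 cases". Enrolment is rounded up to 350. No power is stated.

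Other sections determine who is counted:

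- **9.4.4.1** bases the primary analysis on a per-protocol population whose members must "have the primary efficacy variable measurements available". Section 9.3 rules out imputation.
- **9.4.4.4** says that after a deviation that could affect outcome, "the data for the affected subject will be censored from the Efficacy and Safety" populations.
- **10.3** defines loss to follow-up as non-response after three documented calls and a certified letter. It lists death, centre termination, voluntary withdrawal and revision or removal as separate reasons for leaving. Revision or removal of the shell and insert "constitutes a failure and study termination for the subject".
- **9.1.4** asks for a 90% confidence interval for the 10-year success rate without naming an estimator, and adds that a Kaplan-Meier curve of dislocation will be shown too.
- **9.4.4.3** puts every implanted case in the survival analysis.

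**The concern.** The allowance in 9.4.2 carries the name of one exit category, while 10.3 and 9.4.4 create several others that can also leave a case without a 10-year result. Patients may be up to 75 at surgery and are followed for 10 years, so some deaths and withdrawals must be expected, yet nothing in the documents budgets for them. The minimum analysed number therefore has less protection than the text suggests.

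The same rules affect the estimate as well as the count. A case that dislocates in year 1 is a known failure whatever happens later. A case that dies or is lost in year 6 without dislocating has no 10-year status and drops out. If the interval in 9.1.4 is for a simple proportion, exits remove mainly successes. With only 3.5 points between the reference rate and the threshold, a downward shift of even half a point matters to whether non-inferiority can be shown.

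**Working it through.** **Inputs from the documents.** Reference rate 97%, margin 3.5 points, threshold 93.5%, one-sided 5% (the lower end of the two-sided 90% interval in 9.1.4), 274 analysed, 20% loss to follow-up, 350 enrolled. Section 3.3 counts only cases that receive the device, so non-implanted patients do not use up the 350.

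**The plan's own figures.**
- Inflation: 274 / (1 − 0.20) = 342.5, rounded up to 343. The arithmetic in 9.4.2 is correct.
- Base size, one-sample score formula: n = [(1.645·√(0.935·0.065) + z·√(0.97·0.03)) / 0.035]². This gives 247, 277 and 318 at 80%, 85% and 90% power. So 274 fits a power of about 85%, but the plan does not say so.

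**Room left for other exits.**
- 350 × 0.80 = 280, and 280 − 274 = 6.
- 6/350 = 1.7% of enrolment, or 6/280 = 2.1% of those not lost.
- Total loss that 350 can absorb: 76/350 = 21.7%.

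Let d be all other unevaluable cases as a share of enrolment. The documents give no value, so d is an assumption. Analysed cases = 350 × (0.80 − d):

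| d | analysed |
|---|---|
| 1% | 276 |
| 2% | 273 |
| 5% | 262 |
| 10% | 245 |
| 15% | 227 |

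**Effect on a proportion in measured cases.** Assumptions not in the documents: true success 97%; exits spread evenly over 10 years and unrelated to dislocation; 70% of dislocations in year 1 and the rest evenly over years 1 to 10; a dislocation seen before exit is kept as a failure.

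With 20% loss only:
- Share of dislocations seen before exit: 0.7 × (1 − 0.20 × 0.05) + 0.3 × (1 − 0.20 × 0.55) = 0.693 + 0.267 = 0.96.
- Failures counted: 350 × 0.03 × 0.96 = 10.1. Successes counted: 350 × 0.97 × 0.80 = 271.6.
- Expected proportion: 271.6 / 281.7 = 96.4%.
- The 281.7 exceeds 280 because about two cases leave after a recorded dislocation. On these assumptions the spare is nearer 8 than 6.

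With 20% loss and 10% deaths, acting independently:
- Still present at 10 years: 0.80 × 0.90 = 0.72.
- Share of dislocations seen: about 0.7 × 0.985 + 0.3 × 0.842 = 0.942.
- Failures counted: 10.5 × 0.942 = 9.9. Successes counted: 339.5 × 0.72 = 244.4.
- Expected proportion: 244.4 / 254.3 = 96.1%.

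Simulating the second scenario gives the same 96.1% for the proportion, with its lower bound clearing 93.5% in about 50% of trials. The Kaplan-Meier estimate averages 97.0% and clears it in about 89%. The choice of interval method moves these two percentages by a few points but leaves the contrast.

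**The case against.** **The 20% may be all-cause.** It is a planning figure for a 10-year period, and 9.4.2 does not refer to the contact rule in 10.3. Read that way, 274 is met with 6 to spare. This stands, and it is why the shortfall is conditional. It does not remove the downward pull on a simple proportion, which appears with 20% exits of any kind.

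**Not every exit loses a case.** A dislocation before death, withdrawal or revision is a known outcome. Only deviations that could affect outcome lead to exclusion. Section 10.3 calls shell and insert revision a failure, and its status for the dislocation endpoint is unclear. All of this stands, so the losses that matter are exits without a prior dislocation, plus exclusions.

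**Kaplan-Meier is already signalled.** Section 7.4 describes the curve as needed for the primary endpoint, and 9.4.4.3 takes in all implanted cases. But 9.1.4 only displays the curve, and 9.4.4.1 ties the primary analysis to a different population. No section makes it the basis of the bound.

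**The bias runs against the device**, so it does not by itself create a false claim of non-inferiority. That is fair under the assumptions used. It remains a distorted estimate and an avoidable loss of the chance to succeed.

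Two stronger readings are tempting, and the documents support neither. One is that 274 will not be reached: this needs loss at the full 20% plus more than 6 other losses, at rates the documents do not give. The other is that falling below 274 in itself lowers the planned power. Section 9.4.2 states no power, and exact binomial power is saw-toothed: with a Clopper-Pearson bound and true success 97% it is 79.6% at 274, but 82.1% at 266 and 84.4% at 258. On the smooth score formula the loss is modest, from 84.6% at 274 to 79.8% at 245.

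**Conclusion.** The point holds in a conditional form. As labelled, the 20% covers loss to follow-up only and leaves 6 of 350 cases (1.7%) for deaths, withdrawals, centre closures, revision terminations without dislocation, and deviation exclusions. If loss reaches 20% and these exceed 6, the 274 minimum is missed. If 20% is all-cause, it is met. The sum in 9.4.2 is correct; what is missing is a statement of what it covers.

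The firmer part concerns the estimator. If 9.1.4 means a simple proportion among cases with the endpoint available, early exits bias the success rate downward. The expected figure is about 96.4% with 20% exits and about 96.1% with a further 10% deaths, against a true 97%. The sizes rest on the assumed timing of dislocations and exits. The direction needs only that seen dislocations are kept, dislocation-free early exits are dropped, and exit is unrelated to dislocation. The change should be made, and it is cheap.

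**What to change.** - **9.1.4:** compute the 90% confidence bound from the 10-year Kaplan-Meier estimate of freedom from dislocation in all implanted cases (the 9.4.4.3 population), and name the interval method. Censor exits at last contact. For loss to follow-up, 10.3 records the date of the sponsor's termination approval, which can fall later and would add unobserved event-free time.
- **9.1.4 and 10.3:** reconcile how a shell or insert revision without dislocation is handled in the primary endpoint.
- **9.4.4.1:** keep the per-protocol proportion as a sensitivity analysis.
- **9.4.2:** say whether 20% is all-cause. If not, replace the 274 minimum with an expected range under stated assumed rates for death, withdrawal, centre closure, revision and deviation exclusions. State the power behind 274.

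Enrolment stays at 350 and no data collection is added. The cost is a change to the wording of the primary estimator and population, which is more than an editorial edit, and a stated analysed number that may look less favourable. Kaplan-Meier also assumes that exits are unrelated to dislocation risk, and the plan should say so.

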# 9.4.3 Interim Analyses and early Stopping Considerations

No interim analysis is planned.

### 9.4.4 Efficacy Patient Populations

### 9.4.4.1 **Efficacy**

#### Per protocol population:

The study population for analysis will include all subjects who receive the Restoration® ADM Acetabular Shell and Restoration® ADM X3® Acetabular Insert and have the primary efficacy variable measurements available. This does not include cases censored from analysis for a reason that may have a significant impact on outcome.

The primary efficacy analysis will be based on the per protocol population.

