# 2 Study Objectives

# 2.1 Efficacy

#### 2.1.1 Primary

The primary objective of this study is to evaluate the success rate of cementless primary total hip replacement (THR) with the Restoration® ADM X3® Acetabular System as compared to the published results of primary THR systems. Success will be defined as absence of femoral head dislocation at 10 years postoperative. It is expected that the survivorship of the Restoration® ADM X3® Acetabular System group will be non-inferior to the survivorship reported in the literature for other primary THR systems.

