#### **Patient Outcomes:**

Pain, function and health related QOL will be compared between the Restoration® ADM X3® Acetabular System and reports in the literature for other primary THR systems and similar dual mobility cups on the market. The SF-12 is a 12 item patient self-assessment evaluating health and general well being. The LEAS is a tool that has been developed and validated to evaluate the level of patient activity. The EQ-5D is a standardized instrument for use as a measure of health outcome. These tools will be used to assess patient health-related QOL and will be collected preoperatively at the 6-week, 1, 2, 3, 4, and 5-year visits.

A Follow-Up Questionnaire will be administered annually in postoperative years 6-10 to assess patient satisfaction and pain, and to capture AEs. This questionnaire will provide the survivorship information necessary to evaluate the primary objective of the study. Patient outcomes data will also be obtained at the 7-year and 10-year time points at investigational sites that choose to bring their subjects back in for these optional visits, in addition to the required Follow-Up Questionnaire described.

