### 7.4 Annual Follow-up Visits

Clinical data will be collected via office visit by the investigator at the following annual postoperative intervals: 1-year, 2-year, 3-year, 4-year and 5-year. Tools for postoperative evaluation will be the HHS, AP pelvis, AP femur and lateral radiographs. Radiographs will also be obtained at 1 year and then annually to 5 years postoperatively.

Patient outcomes data will also be collected with the required SF-12, LEAS, and EQ-5D patient questionnaires at each annual visit at the 1-year through 5-year follow-up visits.

All clinical data, radiographs, and patient outcomes data must be collected within  $\pm$  2 months of the 1-year and 2-year anniversary dates. For remaining annual time points, the window expands to  $\pm$  3 months of the 3-year anniversary date and  $\pm$  4 months of the 4-year through 10-year anniversary dates.

The initial phase of the study will continue for 5 years after surgery and include collection of the previously described radiographs, HHS, SF-12, LEAS and EQ-5D patient questionnaires. In the second phase of the study, all subjects will complete a brief Follow-up Questionnaire annually at the 6-year, 7-year, 8-year, 9-year and 10-year follow-up intervals. This form may be completed by the SC during a subject telephone interview, or by the subject either at home or during a clinic visit. The questionnaire will be used to obtain the following information, at a minimum:

- Subject satisfaction with the hip replacement
- Presence of any pain in the study hip
- Any surgeries performed on the study hip
- Any dislocations in the study hip

The questionnaire will also provide information on any revisions and enable calculation of the Kaplan-Meier Survival Curve necessary to meet the primary endpoint of the study.

Additionally, at investigational sites that choose to continue collecting clinical and radiographic data during the second phase of the study, subjects will be evaluated again at 7 and 10 years after surgery.

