### 9.1.4 Primary Efficacy Analysis

A case success is defined as no incidence of postoperative femoral head dislocation within 10 years. A 90% confidence interval of the success rate will be computed at 10 years postoperative. If the lower bound of this confidence interval is greater than 93.5%, the non-inferiority hypothesis will be supported. If the lower bound of this confidence interval is above 97%, the superiority hypothesis will be supported. The Kaplan-Meier survival curve of femoral head dislocation for any reason will also be displayed using SAS/PROC LIFETEST.

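### The estimator behind the 93.5% and 97% decisions is not named; base them on the Kaplan-Meier 10-year dislocation-free rate

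*Combined protocol and SAP*

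**What the plan says.** The statistical sections point to a proportion:

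- Section 9.1.4 defines a binary outcome: "A case success is defined as no incidence of postoperative femoral head dislocation within 10 years". The lower limit of a 90% interval for the success rate is compared with 93.5% (non-inferiority) and 97% (superiority). The curve comes as an addition: "The Kaplan-Meier survival curve of femoral head dislocation for any reason will also be displayed using SAS/PROC LIFETEST".
- Section 9.4.4.1 bases the primary analysis on the per protocol set, meaning subjects with shell and insert who "have the primary efficacy variable measurements available".
- Section 9.3: "No missing data will be imputed for the primary analysis and secondary analyses".
- Section 9.4.2 needs 274 analysed cases. "By factoring in a 20% lost to follow-up rate within a 10-year period" brings this to 343, and 350 are enrolled.

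Other sections point to survival analysis:

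- Section 2.1.1 expects that survivorship "will be non-inferior to the survivorship reported in the literature for other primary THR systems".
- Section 2.1.2, Patient Outcomes, on the questionnaire of years 6-10: "This questionnaire will provide the survivorship information necessary to evaluate the primary objective of the study".
- Section 7.4 says the questionnaire will "enable calculation of the Kaplan-Meier Survival Curve necessary to meet the primary endpoint of the study".
- Section 9.4.4.3 gives the survival analysis a different population: all enrolled subjects who received shell and insert.

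Under section 10.3, revision or removal of shell and insert is a failure and ends participation. Section 11.6 lists an unavailable primary endpoint among the visit deviations.

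**The concern.** The plan does not say what happens to a hip that leaves before year 10, and two readings of availability give different denominators.

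- **Natural reading.** A hip with a recorded dislocation has its endpoint and counts as a failure. An event-free hip lost at year 4 has no 10-year status and is dropped. Failures are kept from the whole cohort and successes only from completers, so the success rate is biased down.
- **Completers-only reading.** Availability is tied to the year-10 contact. The proportion is unbiased if exit is unrelated to dislocation. It is biased up if dislocated hips leave more often, for example through shell/insert revision.

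The first costs power; the second can inflate the false non-inferiority rate. The study is single-arm and unblinded, so an estimator left open could be chosen after the results are visible.

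**Working it through.** **Inputs.** From the documents: null 93.5%, design rate 97%, 90% interval (one-sided 5%), 274 analysed, 20% loss, 350 enrolled. Assumed: timing of dislocation, timing of loss, and exit shares by revision, none of which the documents give.

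**1. The plan's own figure.** For one binomial proportion with one-sided alpha 0.05 and 80% power (power is not stated in 9.4.2):

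n = (1.645·√(0.935·0.065) + 0.842·√(0.97·0.03))² / 0.035² = 246.1

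With continuity correction, n/4·(1 + √(1 + 2/(n·0.035)))² = 273.9, so 274; and 274/0.8 = 342.5, so 343. The sample size therefore fits a binomial analysis. Exact power at 97% with complete data is 79.6% for 274 hips (10 failures allowed) and 86.0% for 280 hips (11 allowed).

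**2. Bias of the natural reading, by hand.** True rate 97%, loss spread evenly over 10 years.

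- Event-free completers: 350 × 0.97 × 0.8 = 271.6.
- All dislocations in year 1: about 1% of hips are lost first, so 350 × 0.03 × 0.99 = 10.4 are recorded. Estimate 271.6/282.0 = 96.3%.
- Dislocations uniform over 10 years: 10% are lost first, so 350 × 0.03 × 0.90 = 9.45. Estimate 271.6/281.05 = 96.6%.

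**3. Chance of passing 93.5%.** Simulation, 350 hips, 20% independent loss, 8,000 runs:

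| True 97%, dislocation timing | Mean, natural reading | Pass, exact | Pass, Wilson | Pass, Kaplan-Meier log-log |
|---|---|---|---|---|
| Uniform | 96.6% | 73% | 75% | 89% |
| 60% in year 1 | 96.5% | 67% | 69% | 90% |
| All in year 1 | 96.3% | 63% | 65% | 90% |

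At a true 93.5% the natural reading passes 0.4-1.5% of the time and Kaplan-Meier log-log 3-5%.

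**4. Completers-only, true 93.5%.** With exit shares d (dislocated) and o (other), the expected estimate is 0.935(1−o) / [0.935(1−o) + 0.065(1−d)].

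| d / o (assumed) | Expected estimate | False non-inferiority, exact bound |
|---|---|---|
| 0 / 0 or 10% / 10% | 93.5% | about 4% |
| 10% / 5% | 0.88825/0.94675 = 93.8% | 5-6% |
| 10% / 0 | 0.935/0.9935 = 94.1% | 8-9% |
| 25% / 5% | 0.88825/0.937 = 94.8% | 17-18% |
| 25% / 0 | 0.935/0.98375 = 95.0% | 23-24% |

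Kaplan-Meier, which keeps every recorded dislocation, stays at 3-5% throughout.

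**5. Two data sets where the verdict flips.** All dislocations precede any loss, so Kaplan-Meier equals events over 350. Normal lower limit: p − 1.645·√(p(1−p)/n). Log-log limit: S raised to exp(1.645·se/(S·|ln S|)).

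- *13 dislocations, 70 event-free hips lost later.* Kaplan-Meier 337/350 = 96.29%; se 0.0101; limit 94.6% normal, 94.2% log-log: passes. Natural reading 267/280 = 95.36%; limit 93.3% normal, 92.8% Wilson, 92.7% exact: fails.
- *20 dislocations, 10 of them revised and terminated, 60 other hips lost later.* Year-10 records 270/280 = 96.43%; limit 94.6% normal, 94.0% exact: passes. Kaplan-Meier 330/350 = 94.29%; se 0.0124; limit 92.2% normal, 91.9% log-log: fails.

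**The case against.** - **A dislocated hip already has its endpoint.** Success is defined within 10 years and dislocation is a dated adverse event, so the completers-only reading is strained, and section 11.6 does not define the analysis set. This stands. The 8-24% rates are illustrations under assumed exit shares; without linked exit the rate is about 4%.
- **The natural reading is conservative.** It stands that this reading is very unlikely to produce a false non-inferiority claim. The harm there is lost power.
- **The loss depends on the bound.** With a normal-approximation bound the natural reading passes 76-85% of the time, close to the 80% that reproduces 274. True, but the like-for-like Kaplan-Meier figure (plain Greenwood) is 93-96%, so the gap remains. Plain Greenwood also has about 7-9% one-sided error, which is why the interval method must be named too.
- **The device may do better than 97%.** At a true 98% (60% of dislocations in year 1) the natural reading with an exact bound passes 95% of the time. So the non-inferiority result is sensitive mainly near 97%, but that is the rate the study was sized on. Power for the superiority comparison was not examined.
- **The section 7.4 sentence starts with revisions**, so its curve could be revision survivorship. This weakens that passage as support for a dislocation curve. It still ties the curve to the primary endpoint, which is dislocation.
- **Naming the proportion and defining availability would also end the ambiguity.** It would, but the natural-reading proportion would stay biased under the loss the plan itself expects.

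**Conclusion.** The concern holds. The sections conflict, and neither estimator nor interval method is fixed for the decision. Under the natural reading with 20% independent loss, the estimate falls 0.4-0.7 percentage points below a true 97%. The chance of passing drops to 63-75% with exact or Wilson bounds, against 89-90% for Kaplan-Meier log-log. Under the completers-only reading the error can go the other way, by an amount that rests on exit shares the documents do not give. Kaplan-Meier avoids both problems when censoring is non-informative. This should be fixed before the 10-year analysis; it does not call for a change in design or sample size.

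**What to change.** Reconcile sections 7.4, 9.1.4, 9.4.4.1, 9.4.4.3 and the synopsis, and state:

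1. **Estimator and limit.** The decision uses the Kaplan-Meier 10-year dislocation-free rate; the lower limit of its log-log 90% interval is compared with 93.5% and 97%.
2. **Events.** Every recorded dislocation is a failure whatever the later follow-up. Say whether intra-prosthetic dislocation, coded separately on the adverse event form, counts.
3. **Censoring.** Censor at the last date dislocation status was known, taken from visit or questionnaire dates. For lost subjects the section 10.3 termination date is the sponsor's approval date, which overstates time at risk.
4. **Population.** All hips that received shell and insert (section 9.4.4.3), dropping the availability condition. Report the result without the section 9.4.4.4 deviation cases as a sensitivity analysis.
5. **Revision without dislocation.** Section 10.3 calls shell/insert revision a failure, while 9.1.4 counts only dislocation. State how it enters.
6. **Other sensitivity analyses.** The available-case proportion with availability defined and an exact or Wilson bound; death and revision without dislocation as competing events; a tipping-point analysis for lost hips.

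The cost is protocol/SAP wording and modest programming. The dislocation curve is already planned, onset is dated on the adverse event form, and dislocation is asked at each questionnaire contact in years 6-10. The small downside is the assumption of non-informative censoring, which item 6 probes.

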#### CONFIDENTIAL

# **Study Synopsis**

	A prospective, post-market, multi-center evaluation of the clinical			
	outcomes of the Restoration® Anatomic Dual Mobility (ADM) X3®			
Title	Acetabular System with Long Term Data Collection for the Accolade®			
	II Hip Stem			
Short Title Restoration® ADM X3® Study				
Protocol Number	70			
Phase	Post-market			
	This study is a prospective, open-label, post-market, non-			
	randomized, multi-center, clinical evaluation of the Restoration® ADM			
	X3 ® Acetabular System for primary total hip arthroplasty (THA) with a			
	cementless application in a consecutive series of patients who meet			
	the eligibility criteria. The total enrollment goal for the study is 350			
Methodology	cases, all of which will receive the Restoration® ADM X3® Acetabular			
	System. A minimum of 100 cases (within the study population) will			
	receive the Accolade® II Hip Stem. The remaining cases will receive			
	any other compatible Stryker femoral component.			
	Data in the literature from other primary hip systems and similar dual			
	mobility cups will be used as historical references.			
	Follow-up of each primary THA case to 10 years			
Study Duration	2. Enrollment period of 24 months			
-	3. Approximate 12-year total duration			
Study Center(s)	Up to 12 investigational centers			

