### 9.4.4.3 Survival Analysis

#### **Modified intent to treat population:**

Subjects enrolled in the study who received the Restoration® ADM Acetabular Shell and Restoration® ADM X3® Acetabular Insert will be included in the survival analysis.

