# 11 Data Management

#### 11.1 Database

Data will be collected at each center and entered into Stryker's Electronic Data Capture (EDC) system, NetRegulus. The system can be accessed remotely by each investigative center and the data entered will be managed by Stryker. Subject data will be processed and monitored according to the protocol schedule by Stryker or Stryker representatives. Draft specifications to support eCRFs are provided in Appendix F.

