### 11.6 Protocol Deviations

Any deviation from this protocol will be reported to Stryker as well as to the EC/IRB according to their reporting procedures. Protocol Deviations for this study include, but are not limited to, the following:

- Informed consent deviations, including but not limited to:
  - Study procedures performed prior to informed consent
  - Incorrect informed consent version used
- Patient enrolled does not meet the inclusion/exclusion criteria
- Protocol specified study component(s) not implanted
- Visit deviations, including:
  - Unavailable primary endpoint
  - One or more required eCRFs/radiographs not done
  - Evaluations occurred outside of protocol specified time window
  - Un-evaluable radiographs
  - Missed visit

If the center anticipates a possible protocol deviation, the investigator or SC should contact Stryker for guidance.

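### The 93.5% and 97% tests run on a per-protocol set whose exclusions have no advance list, decision-maker, timing or blinding to dislocation status

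*Combined protocol and SAP*

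**What the plan says.** Section 9.1.4 compares the lower end of a 90% confidence interval for 10-year freedom from dislocation with 93.5% (non-inferiority) and 97% (superiority). On the analysis set, 9.4.4.1 states: "The primary efficacy analysis will be based on the per protocol population". That set holds subjects who received the shell and insert and have the primary variable available, with one carve-out: "This does not include cases censored from analysis for a reason that may have a significant impact on outcome".

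Section 9.4.4.4 gives the trigger: "In the event that a protocol deviation occurs which could affect subject outcome, the data for the affected subject will be censored". The removal covers both the efficacy and the safety sets. The catalogue of deviations in 11.6 is open-ended ("Protocol Deviations for this study include, but are not limited to, the following"). It runs from consent and eligibility breaches to missed or out-of-window visits.

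Two provisions temper this. Section 9.4.4.4 has the removed cases reported separately. Section 9.4.4.3 defines a modified intent-to-treat set of enrolled subjects with the shell and insert, who "will be included in the survival analysis", and 9.1.4 has a Kaplan-Meier curve of dislocation displayed.

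**The concern.** The rule that decides who counts in the primary test is left to judgement, and the criterion for that judgement is itself framed around effect on outcome. The plan does not say which deviations qualify, who decides, at what point in the 10 years, or whether dislocation status is withheld from that person. The synopsis describes the study as open-label, centers record dislocations, and 11.1 says of the data system: "The system can be accessed remotely by each investigative center and the data entered will be managed by Stryker".

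A per-protocol set is often preferred in a two-arm non-inferiority trial because protocol departures can pull the arms together. Here one arm is held against a fixed limit, so that argument has nothing to act on. What remains is a confirmatory verdict resting on about ten events and an unspecified exclusion step. The displayed curve, drawn on all recipients, could disagree with the test, and no rule says which prevails.

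**Working it through.** **Inputs.** From 9.4.2: expected success 97%, margin 3.5 points (limit 93.5%), one-sided 95% confidence, 274 cases analyzed, 20% loss to follow-up, 350 enrolled. The 90% two-sided interval in 9.1.4 has the same lower bound as the one-sided 95% interval. Power and interval method are not stated. I assume 80% power to reproduce the sample size and use the exact (Clopper-Pearson) interval as the base case.

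**The plan's own figure.** One-sample test of a proportion:

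n = [1.645·√(0.935·0.065) + 0.842·√(0.97·0.03)]² / 0.035² = 246.1.

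With continuity correction, (n/4)·[1 + √(1 + 2/(n·0.035))]² = 273.9, so 274. Then 274/0.80 = 342.5, so 343. Both stated figures reproduce.

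**Sensitivity to one case.** The exact lower bound for f dislocations in n cases is the 5% quantile of Beta(n − f, f + 1).

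- 10/274: 93.89%, passes 93.5%.
- 11/274: 93.44%, fails. Remove one dislocated case: 10/273, 93.87%, passes.
- Same step with 350 cases: 15/350, 93.48%, fails; 14/349, 93.80%, passes.
- Superiority limit of 97%: 4/274, 96.69%, fails; 3/273, 97.18%, passes.

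The one-case flip at 93.5% does not depend on the unnamed interval method:

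- Wilson: 12/274 = 93.10% fails, 11/273 = 93.52% passes.
- Wald: 13/274 = 93.14% fails, 12/273 = 93.56% passes.
- Jeffreys: 12/274 = 93.22% fails, 11/273 = 93.64% passes.

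**Sensitivity in the other direction.** Removing non-dislocated cases lowers the bound. Starting from a pass at 10/274, removing 17 such cases (17/274 = 6.2%) gives 10/257 and a bound of 93.49%, which fails.

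**Error rate, worst case.** With 274 cases the exact test passes at 10 dislocations or fewer. At a true success rate of 93.5%, with X binomial(274, 0.065):

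- No removals: P(X ≤ 10) = 2.9%.
- One dislocated case always dropped when needed: P(X ≤ 11) = 5.4%.
- Two always dropped when needed: P(X ≤ 12) = 9.1%.

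**Error rate when a case can be dropped only if it has a deviation.** The documents give no deviation rate. I assume 5-10% of cases, independent of outcome.

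- At most one dislocated case dropped: P(X ≤ 10) + P(X = 11)·[1 − (1 − d)¹¹]. With P(X = 11) = 2.46%, this is 2.92% + 2.46%·0.431 = 4.0% at d = 5%, and 2.92% + 2.46%·0.686 = 4.6% at d = 10%.
- Every dislocated case with a deviation dropped and no other case: summing over X and the number dropped, 4.6% at d = 5% and 7.0% at d = 10%.

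**The case against.** The strongest reply is that nothing in the documents says exclusions will be decided with outcomes in view. A reader might infer outcome-aware exclusion from the open-label design and the publications anticipated at 2 and 5 years in section 16, but no section says when or by whom the decision is made. Several deviations in 11.6 (consent, eligibility, components) are settled by the time of surgery, before any postoperative dislocation, and the deviation form in Appendix F is dated. That stands: the supported statement is that no safeguard is specified.

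A reader might also infer that the rule can only favour the device. It cannot be read that way, because 9.4.4.4 removes deviating cases whatever their outcome, and 10/257 shows the harm this can do. If exclusion is unrelated to outcome, the exact test keeps its error below 5% at whatever size remains.

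The 5.4% and 9.1% figures need a dislocated case with a qualifying deviation to be always available and always dropped while successes stay in. The 2.9% baseline also reflects the conservatism of the exact interval: with no exclusions at all, Wilson gives 5.4% and Wald 9.1%. Any binary test flips on one event at its boundary, and the chance of landing on exactly 11 is 2.5% at a true 93.5% and 7.9% at 97%. All of this stands as a limit on size.

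The separate reporting and the all-recipient curve are real mitigation, and 7.4 even links a Kaplan-Meier curve to the primary endpoint. But 9.1.4 only displays the dislocation curve. Neither item is compared with 93.5% or 97%, and no repeat of the test on all implanted cases is planned.

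**Conclusion.** The concern holds as a gap in specification, at should-fix level. The primary verdict rests on a set whose exclusions are not prespecified or blinded, in a design where the usual reason for a per-protocol set is absent. One excluded case can reverse the result at the boundary, in either the 93.5% or the 97% comparison.

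Inflation of false non-inferiority requires selective removal of dislocated cases. It is then at most 5.4% (one removal) or 9.1% (two) against 2.9%, or about 4.0-7.0% if only cases with a deviation can be dropped. These figures assume 274 analyzed cases and the exact interval; the last range also assumes deviations in 5-10% of cases, independent of outcome. They measure exposure and are not a forecast. The documents do not support saying that exclusions will be made with knowledge of dislocations, or that they must favour the device.

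**What to change.** In 9.4.4.1, apply the 93.5% and 97% rule to all cases that received the shell and insert, with no removal for deviations. Because 9.4.2 expects 20% loss and 9.3 rules out imputation, the text must also say how incomplete follow-up is handled. Two options fit the plan:

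- (a) the 10-year Kaplan-Meier estimate of freedom from dislocation, with its 90% confidence interval, on the 9.4.4.3 set; or
- (b) the proportion among all implanted cases with a known 10-year outcome, counting any earlier dislocation as a failure.

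State which one governs. Keep the per-protocol set as a sensitivity analysis, with qualifying deviations listed in advance and each case judged without knowledge of dislocation status. Show the number of dislocations among excluded cases beside the primary result, which builds on the separate reporting already promised in 9.4.4.4.

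The cost is revised wording and a little extra analysis; no new data, visits or patients are needed. The estimate may be slightly less favourable.
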